1.1. Objectives, Endpoints, and Estimands

Objectives and endpoints are listed in Table 1–1.

Table 1–1: Objectives and endpoints

Objectives	Endpoints
Primary	
To evaluate the efficacy of elinzanetant for the treatment of VMS caused by adjuvant endocrine therapy in women with, or at high risk for developing hormone-receptor positive breast cancer	 Primary endpoints Mean change in frequency of moderate to severe HF from baseline to Week 4 (assessed by HFDD) Mean change in frequency of moderate to severe HF from baseline to Week 12 (assessed by HFDD) Secondary endpoints Mean change in severity of moderate to severe HF from baseline to Week 4 (assessed by HFDD) Mean change in severity of moderate to severe HF from baseline to Week 12 (assessed by HFDD) Exploratory endpoints: Proportion of participants with at least 50% reduction in frequency of moderate to severe HF at Week 4 Proportion of participants with at least 50% reduction in frequency of moderate to severe HF at Week 12

ersion 3.0 Page: 12 of 87

Objectives	Endpoints	
Secondary	Zinapointo	
To evaluate the onset of efficacy of elinzanetant for the treatment of VMS caused by adjuvant endocrine therapy in women with, or at high risk for developing hormone-receptor positive breast cancer	Secondary endpoints: • Mean change in frequency of moderate to severe HF from baseline to Week 1 (assessed by HFDD) • Mean change in frequency of moderate to severe HF from baseline over time (assessed by HFDD) Exploratory endpoints: • Time to treatment response* • Mean change in frequency of mild, moderate, and severe HF from baseline over time (assessed by HFDD)**	
To evaluate the	Key secondary endpoints:	
efficacy of elinzanetant in women with, or at high risk for developing hormone-receptor	Mean change in PROMIS SD SF 8b total T-score from baseline to Week 12 Mean change in MENQOL total score from baseline to Week 12	
positive breast cancer	Exploratory endpoints:	
positive breast cancer on:	 Absolute values and changes from baseline in the PROMIS SD SF 8b total T-and total raw scores over time Absolute values and changes from baseline in MENQOL total, domain and single item scores over time Absolute values and changes from baseline in the ISI total score over time Absolute values and changes from baseline in EQ-5D-5L single dimensions and health state VAS score over time. Absolute values and changes from baseline in SF-36 v2.0 Acute domain, physical component summary (PCS) and mental component summary (MCS) scores over time Absolute values and changes from baseline in the BDI-II total score over time Mean change in frequency of nighttime awakening from baseline over time (assessed by HFDD)** Mean change in proportion of days with participants rating of "quite a bit" or "very much" sleep disturbances experienced due to HF from baseline over time (assessed by HFDD)** 	
To evaluate the safety of elinzanetant for the treatment of VMS caused by adjuvant endocrine therapy in women with, or at high risk for developing hormone-receptor positive breast cancer Other pre-specified To evaluate variability	Other endpoints: Number of participants with TEAEs Number of participants with abnormal laboratory parameters Mean change in Sleepiness Scale, at Week 1, Week 4, Week 12, Week 26, Week 36 and Week 50 compared to baseline Systemic exposure of elinzanetant in plasma via sparse PK sampling	
in exposure in relation to the efficacy and safety for elinzanetant	Systems exposure of omizanetant in plasma via oparoc in Camping	

version 3.0 Page: 13 of 87

Objectives	Endpoints
To further investigate elinzanetant (e.g., mode-of-action-related effects, safety) and to further investigate pathomechanisms deemed relevant to VMS caused by adjuvant endocrine therapy and associated health problems	Various biomarkers (e.g., diagnostic, safety, pharmacodynamic, monitoring, or potentially predictive biomarkers)

BDI-II=Beck Depression Inventory, EQ-5D-5L=European Quality of Life 5-dimension 5-level questionnaire, HF = Hot Flash, HFDD=Hot Flash Daily Diary, ISI=Insomnia Severity Index, MENQOL=Menopause Specific Quality of Life Scale, PK = Pharmacokinetics, PROMIS SD SF 8b=Patient-reported Outcomes Measurement Information System Sleep Disturbance Short Form 8b, SAP = Statistical analysis plan, SF-36 v2.0 Acute = Short Form-36 Health Survey Version 2.0 Acute, TEAE = treatment emergent adverse event, VAS = Visual analog scale,

VMS = Vasomotor symptoms

^{*}Please see Section 4.4.1 for the definition of treatment response.

^{**}Exploratory endpoints in addition to listed in the protocol.

version 3.0 Page: 14 of 87

Estimands

The attributes of the main estimand for the primary endpoints are as following:

- Population: women aged 18-70 with VMS caused by adjuvant endocrine therapy, as described by the inclusion/exclusion criteria detailed in the protocol.
- Variable: Efficacy will be assessed based on 2 primary endpoints as listed below:
 - o Change in frequency of moderate to severe HFs from baseline to Week 4
 - o Change in frequency of moderate to severe HFs from baseline to Week 12.
- Treatment: 120 mg elinzanetant, placebo
- ICEs: see Table 1–2 (for further details regarding the identification of ICEs see Section 6.4)

Table 1-2: Primary Estimand: ICEs and Strategies to Address Them

ICEs ^a	Reason for ICE	Strategy	Data handling method
Temporary Treatment interruption ^b	AEs (treatment related/unrelated)	Treatment policy	Utilise the collected data after ICE.
	COVID-19 and administrative reasons	Treatment policy	Utilise the collected data after ICE.
Permanent discontinuation of randomized treatment	AEs (treatment related/unrelated) or Lack of efficacy		
	 For participants who remained untreated/on background therapy. 	Treatment policy	Utilise the collected data after ICE.
	 For participants who initiate alternative VMS treatment 	Treatment policy	Utilise the collected data after ICE.
	Other treatment- unrelated reasons, including COVID-19	Treatment policy	Utilise the collected data after ICE.
Intake of prohibited concomitant medication having impact on efficacy	All reasons	Treatment policy	Utilise the collected data after ICE.
Interruption/ discontinuation in intake of adjuvant endocrine therapy ^c	All reasons	Treatment policy	Utilise the collected data after ICE.

version 3.0 Page: 15 of 87

Table 1-2: Primary Estimand: ICEs and Strategies to Address Them

ICEs ^a	Reason for ICE	Strategy	Data handling method
AE = Adverse ev	ent, COVID-19 = Corona	virus disease	of 2019, ICE = Intercurrent event, VMS =
Vacomotor e	vmntome		

- a) ICEs will be reviewed at the Blinded Review Meeting prior to the study unblinding
- b) Definition of temporary treatment interruption:
- Week 1 = Treatment taken on <5/7 days during week 1 (day 2-8).
- Week 4 = Treatment taken <80% during weeks 1-4 (day 1-28) OR treatment taken on <5/7 days during either Week 3 or 4.
- Week 8 = Treatment taken <80% during weeks 1-8 (day 1-56) OR treatment taken on <5/7 days during either week 7 or 8.
- Week 12 = Treatment taken <80% during weeks 1-12 (day 1-84) OR treatment taken on <5/7 days during either Week 11 or 12.
- c) Definition of interruption/discontinuation in intake of adjuvant endocrine therapy:
- For participants using tamoxifen: reduction of at least 50% of planned daily dosage taken during week 1, weeks 3 and 4, week 7 and 8 or weeks 11 and 12 compared to baseline
- For participants using aromatase inhibitor: reduction of at least 30% of planned daily dosage taken during week1, weeks 3 and 4, week 7 and 8 or weeks 11 and 12 compared to baseline
- Population level summary:
 - o Mean change in frequency of moderate to severe HFs from baseline to Week 4.
 - Mean change in frequency of moderate to severe HFs from baseline to Week
 12.

The key secondary endpoints will be handled using similar attributes except for the variables and population summary that are listed below:

[figure not shown]
- Variable:
 - o Change in PROMIS SD SF 8b total score from baseline to Week 12
 - o Change in MENQOL total score from baseline to Week 12
- Population level summary:
 - o Mean change in PROMIS SD SF 8b total score from baseline to Week 12
 - o Mean change in MENQOL total score from baseline to Week 12.

Treatment comparison will be based on differences in treatment group means.

version 3.0 Page: 16 of 87

[figure not shown]
1.2. Study Design

Figure 1-1: Study Schema participants not entering the 2 year treatment extension

Approx. = approximately, ICF = Signing of informed consent form, Rand. = randomization
After completion of Part A the final efficacy analysis and a safety assessment will be performed.

Figure 1–2: Study Schema for participants entering the 2 year treatment extension

Approx. = approximately, ICF = Signing of informed consent form, Rand. = randomization
After completion of Part A the final efficacy analysis and a safety assessment will be performed.

- Multi-center, multi-country, double-blind, randomized, parallel-group, placebocontrolled, Phase 3 intervention study in post-menopausal women, or at high risk for developing hormone-receptor positive breast cancer.
- Total study duration for all participants: approximately 62 weeks (plus potential washout period), including
 - Washout period (if applicable)

After giving informed consent, but before starting formal screening procedures, participants will be withdrawn from prohibited concomitant medications.

- Screening: approximately 6 weeks
- o Treatment: 52 weeks
- o Follow-up: 4 weeks
- Visit Frequency: Every 4-6 weeks
- Participants will be randomized 2:1 to either Elinzanetant 120 mg for 52 weeks or Placebo for 12 weeks, followed by elinzanetant 120 mg for 40 weeks

version 3.0 Page: 17 of 87

Randomization will be stratified by women with breast cancer or high-risk for developing breast cancer and by type of treatment for the pre-existing condition at baseline (participants on tamoxifen and participants on aromatase inhibitors). The participant should be on stable adjuvant endocrine therapy at least 6 weeks prior to baseline.

The analysis of part A is planned after the last participant completed part A (visit T9). This will be the final analysis for efficacy and safety of part A data and be based on cleaned and final data. Data from Part B will not be included in this analysis. Part B data will be analyzed together with Part A data after completion of the study (all subjects completed T13/End of treatment (EoT) and follow-up).

Participants who complete the 52 weeks treatment phase will be offered to continue treatment for another 2 years treatment extension (part C). Visit frequency: every 24 weeks until week 156. Part C will be analyzed separately.

version 3.0 Page: 18 of 87

2. Statistical Hypotheses

The hypotheses for the primary efficacy endpoints are defined as:

- **H1-** H_{01} : $\mu_{1P} \le \mu_{1V}$ versus H_{11} : $\mu_{1P} > \mu_{1V}$ where μ_{1P} and μ_{1V} stand for the mean change from baseline in the placebo (P) and verum (V) group in HF frequency at week 4.
- **H2-** H_{02} : $\mu_{2P} \le \mu_{2V}$ versus H_{12} : $\mu_{2P} > \mu_{2V}$ where μ_{2P} and μ_{2V} stand for the mean change from baseline in the placebo (P) and verum (V) group in HF frequency at week 12.

The hypotheses for the key secondary efficacy endpoints are defined as:

- **H3-** H_{03} : $\mu_{3P} \le \mu_{3V}$ versus H_{13} : $\mu_{3P} > \mu_{3V}$ where μ_{3P} and μ_{3V} stand for the mean change from baseline in the placebo (P) and verum (V) group in PROMIS SD SF 8b total score at week 12.
- **H4-** H_{04} : $\mu_{4P} \le \mu_{4V}$ versus H_{14} : $\mu_{4P} > \mu_{4V}$ where μ_{4P} and μ_{4V} stand for the mean change from baseline in the placebo (P) and verum (V) group in MENQOL total score at week 12.

For the confirmatory efficacy analysis, a hierarchical testing approach will be applied, involving the two primary efficacy variables and the two key secondary variables.

The type I error rate will be controlled at a one-sided α =0.025 level. For a positive study outcome, both tests for primary variables need to be significant.

2.1. Multiplicity Adjustment

As the hierarchical testing procedure follows a fixed sequence, it stops as soon as any of tests listed above cannot be rejected at an alpha level of 0.025 and all further tests after failing to reject one null hypothesis in the testing sequence will be considered exploratory. This fixed sequence procedure accounts for the multiplicity created by carrying out multiple tests. Moreover, all other endpoints will be summarized descriptively and therefore no multiplicity adjustment is needed.

version 3.0 Page: 19 of 87

3. Analysis Sets

For the purposes of analysis, the following analysis sets are defined in Table 3–1: Definition of analysis sets.

Table 3-1: Definition of analysis sets

Analysis Set	Description
Enrolled	All participants who sign the informed consent form.
Full Analysis Set (FAS)	All randomized participants.
Safety Analysis Set (SAF)	All participants who receive at least one dose of study intervention.

Efficacy analyses will be based on the FAS and participants will be analyzed according to the randomized intervention. Safety analyses will be performed on the SAF and participants will be analyzed according to the intervention received.

In case of mis-randomization using wrong strata occurs, the correct stratification factors will be used in the analyses. In case more than 5 % are stratified incorrectly a sensitivity analysis for primary endpoints will be performed using randomized stratum.

Documentation of validity findings and assignment of participants to analysis sets will be performed according to the sponsor's applicable Standard Operating Procedures.

Final decisions regarding the assignment of participants to analysis sets will be made during the review of study data and documented in the final list of important deviations, validity findings and assignment to analysis set(s).

Tables that are pre-specified to be displayed for FAS and SAF may be displayed for the FAS exclusively in case both analysis sets as well as the randomized intervention and the actual intervention received are identical.

version 3.0 Page: 20 of 87

4. Statistical Analyses

4.1. General Considerations

For a detailed description of the testing procedure including adjustments to the significance level, please see Section 2. The overall type I error rate will be controlled at 2.5 % one-sided. In general, confidence intervals (CI) will be two-sided with a confidence level of 95%.

The statistical evaluation will be performed by using the software SAS (release 9.4 or higher; SAS Institute Inc., Cary, NC, USA).

All variables will be analyzed by descriptive statistical methods. The number of data available and missing data, mean, standard deviation, minimum, median, and maximum will be calculated for metric data. The geometric mean and geometric SD will be provided instead of the arithmetic mean and SD for variables where lognormal distributions are assumed. Frequency tables will be generated for categorical data. Where appropriate, the data will also be presented by visit or week, including the analysis of the changes from baseline.

Variables recorded in the electronic case report form (eCRF) and relevant derived variables will be shown in subject data listings, whereby only randomized patients will be included. All data will be presented in the participant data listing as they are recorded on the eCRF, i.e., partially missing data will appear as such. Data from screening failures will only be shown in the 'Screening failure' listing.

Number of decimal places for summary statistics will be the following:

Table 4-1: Number of decimal places for summary statistics

Statistic	Number of digits
Minimum, maximum	Same as original data
Mean, median	1 more than in original data
SD	1 more than in original data
Frequencies (%)	1 digit
p-values	4 digits

4.1.1. Handling of Missing Data

This section describes the general handling of missing data. This includes data that would be meaningful for the analysis in terms of the study objectives but were not collected. The rules for handling the data that do not exist or are not considered meaningful for the analysis, because of an intercurrent event, are described in Section 4.2.1 and 4.2.3. No imputation of missing assessments will be performed for the secondary and exploratory endpoints unless it is specified otherwise.

All missing or partial data will be presented in the subject data listing as they are recorded on the eCRF or electronic diary (eDiary).

version 3.0 Page: 21 of 87

For the computation of durations, i.e., time between start and end date of certain events, and concomitant medication intake, a complete date is necessary.

The following rule will be applied to impute the missing start or end date of adverse events (AE)/ concomitant medications (CM)/procedures:

An imputation range will be defined as the earliest possible date (lower range) and the latest possible date (upper range) of the occurrence of AE/CM/procedures. If AE/CM/procedures end date is available, this will be used as the latest possible AE/CM/procedures occurrence date in the imputation range.

If the active treatment start date falls within imputation range, incomplete AE/CM/procedures start date will be imputed as the active treatment start date. If the active treatment start date does not fall within the imputation range, and the placebo treatment start date falls within the imputation range, an incomplete AE/CM/procedures start date is imputed as the placebo treatment start date. Otherwise, the partially missing AE/CM/procedures start date will be imputed to the earliest date of the imputation range. Completely missing start date will not be imputed. According to worst case criteria if there are completely missing AE/CM start dates, those AEs are considered treatment emergent and CMs as concomitant.

Partially missing AE/CM/procedures end date will be imputed as the latest possible date of AE/CM/procedures imputation range. Completely missing end date will not be imputed and presumed to be ongoing.

Missing start dates in certain events (for example date of initial diagnosis) will be imputed by replacing the missing information on the day and month of the event with the first day of the month and the first month of the year.

The date of permanent discontinuation of study medication will be collected in eCRF. In case of missing date, it will be determined based on last medication intake date before the discontinuation using available eDiary data.

Unless specified otherwise, participants with missing baseline assessments will be excluded from all analyses that require the respective baseline assessment.

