# 6.1 Study Intervention(s) Administered

Table 6-1: Study Intervention(s) Administered

Intervention Label	Elinzanetant	Placebo
Intervention Name	BAY 3427080 / elinzanetant	Placebo
Intervention Description	60 mg capsule, 120 mg, qd	two capsules, qd
Туре	Drug	N/A
Dose Formulation	soft gel capsule	soft gel capsule
Unit Dose Strength(s)	60 mg	N/A
Dosage Level(s)	two capsules daily (120 mg)	two capsules daily
Route of Administration	oral	oral
Use	experimental	placebo
Packaging and Labeling	Study Intervention will be provided in an Alu-Alu blister with 12 soft gel capsules. 5 blisters will be placed into 1 box containing capsules for treatment of one month. Each box will be labeled as required per country requirement	Study Intervention will be provided in an Alu-Alu blister with 12 soft gel capsules. 5 blisters will be placed into 1 box containing capsules for treatment of one month.  Each box will be labeled as required per country requirement
Current	BAY 3427080	N/A
Former Name	NT-814	

Alu = Aluminium; N/A = Not applicable; qd = Once daily

Table 6-2: Study Arm(s)

Arm Title	Elinzanetant	Placebo
Arm Type	experimental	placebo
Arm Description	Participants will receive 120 mg elinzanetant orally once daily for 52 weeks and optionally for additional 2 years.	Participants will receive placebo orally once daily for the first 12 weeks. 120 mg elinzanetant will be administered from week 13 to 52 and optionally for additional 2 years.
Associated Intervention Labels	Elinzanetant	Placebo or Elinzanetant

Study intervention will be dispensed at the study visits summarized in the SoA.

The first dose should be taken supervised during the Baseline Visit on the day of randomization. In general, study treatment will be taken once daily before going to bed in both treatment arms, with or without food. For requirements on drug intake for PK sampling, please refer to Section 1.3.4.

If a participant forgets to take a dose in the evening, then the dose can be taken at any time up to 2AM the same night. After this time, the dose should not be taken and will be considered a missed dose.

Returned study intervention may not be re-dispensed to a different participant.

10 MAY 2023 Page: 35 of 97

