4.1.2. Data Rules

Definition of baseline: The latest available valid measurement excluding unscheduled measurements at or before the start of treatment (for treated subjects) / randomization date (for randomized but not treated subjects). If the last observation available prior to randomization is the measurement from the Screening Visit, this would be used as the baseline value. In case a wash-out period was necessary, measurements taken during the prescreening visit will not be used as a baseline value unless specified otherwise.

Change from baseline: To calculate the absolute change from baseline the baseline value will be subtracted from the value under treatment/follow-up, i.e.,

Absolute change = post baseline value – baseline value.

Some parameters will be additionally analyzed as relative change defined as

Relative change = 100 * [(post baseline value – baseline value) / baseline value].

Derivation of intercurrent event (ICE): Intercurrent events that occurred from randomization date (for randomized but not treated subjects) / start of treatment (for treated subjects) to day 84 inclusive will be flagged.

version 3.0 Page: 24 of 87

For the "permanent discontinuation of randomized drug", "intake of prohibited medication having impact on efficacy" and "interruption/ discontinuation in intake of adjuvant endocrine therapy", if the ICE occurs on or before the 5th day of the week, it will be flagged for the respective week. If the ICE occurs on the 6th or 7th day of the week, it will be flagged from the following week. For example, if the participant permanently discontinues from the randomized drug on the 2nd day of week 4, the ICE will be flagged from week 4 onwards. If the discontinuation from the randomized drug occurs on the 6th day of week 4, then the ICE will be flagged from week 5 onwards. For the ICEs "intake of prohibited medication having impact on efficacy" and "interruption/ discontinuation in intake of adjuvant endocrine therapy", if the end date for the impact on efficacy occurs on the 1st or 2nd day of the week, the respective week should not be flagged. If the end date of impact on efficacy occurs on or after the 3rd day of the week, the week should be flagged.

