The imputation will be done using a regression model (PROC MI with MONOTONE REG) including covariates described above for each time point and using the MNAR statement to estimate the model from placebo participants only.

To impute missing data for participants randomized to placebo, using MAR assumption, the imputation will be done using a regression model including measurements from all timepoints before the time-point being imputed in addition to baseline measurement and the stratification factor (PROC MI with MONOTONE REG).

PROC MI will be run with the random seed setting SEED=21656 to produce 500 imputed datasets.

After the completion of imputation step, change from baseline values will be calculated and each imputed dataset will be analyzed using the MMRM model specified in Table 4–3 to obtain an estimate of the mean change from baseline and of the treatment effect. The results will be combined using the Rubin's rule (Rubin, 1987) to obtain an overall estimated mean change from baseline and an overall estimated treatment effect. A total of 500 multiple imputation steps will be used.

Details regarding how the ICEs will be identified and specifics regarding the reasons for the occurrence of ICE are described in Section 6.4. All the ICEs will be reviewed prior to study unblinding.

The results from the main analysis will be presented as the number of participants, estimated mean change from baseline and standard error (SE) for each treatment group at Weeks 4 and 12 as well as the estimated treatment difference (elinzanetant - placebo), SE of the difference, associated 95% CI and P-value (one-sided). A plot of the model-based estimates with SE will be provided by the treatment for Weeks 4 & 12.

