6.4.3. Intake of prohibited concomitant medication having impact on efficacy

Drug groupings, individual drugs and manual review will be used to identify whether any prohibited concomitant medication as defined in the protocol were used that influence efficacy. All here listed drug groupings/ drug names were reported in OASIS 1-4 studies as of finalization of this statistical analysis plan, although other medications may also be prohibited per the protocol.

- 1. For the change from baseline at Week 1 any intake of prohibited medication during Week 1 that has an effect on HF will be considered an intercurrent event.
- 2. For weeks 4, 8, and 12, not only intake in the respective week but also, intake that occurred prior to week 4, 8, and 12 should be considered as an intercurrent event if within the washout period of the prohibited drug.

A similar approach will be used for the endpoints related to sleep quality (mean change in PROMIS SD SF 8b total score from baseline) and to the menopause related quality of life (mean change in MENQOL total score from baseline) with respect to any prohibited medication that has an effect on sleep quality and menopause related quality of life, respectively.

The list of prohibited concomitant medication together with the assumed relevant time period for their effect will be reviewed during blind review of the data and finalized prior to unblinding.

^b No further differentiation if duration of impact is longer than 12 weeks since ICEs are considered in the analysis only for the first 12 weeks of the study.

version 3.0 Page: 73 of 87

Table 6–5: Preliminary list of prohibited concomitant medication by drug grouping (can be updated during the blind review meeting)

Any additional condition, so that considere d as prohibite d and considere d as intercurre nt event	DGCODEL0	DGNA ME0	DGCODE L1	DGNAME1	DGCODEL2	DGNAME2	Duration of impact with respect to efficacy ^a (considered up to 12 weeks ^b)
If newly started or dose modified or stopped during the first 12 weeks of study period			5	Hormone replacement therapy	2	Oestrogens	1, From 1st dose to 4 weeks after the last dose if the route is vaginal, intravaginal, cutaneous, nasal or transdermal. 2, From 1st dose to 8 weeks after the last dose if the route is oral, sublingual or intrauterine, 3, From 1st dose to 12 weeks or longer if the route is subcutaneous or intradermal.

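### The partial-date rule for concomitant drugs uses an arm-dependent anchor, so a prohibited drug dated only to the switch month or switch year can be a Week 12 intercurrent event on elinzanetant but not on placebo

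*SAP*

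**What the plan says.** SAP 4.1.1 (Handling of Missing Data) gives one rule for partial start dates of adverse events, concomitant medication and procedures. A range of possible dates is set up, and a known end date shortens it: "If AE/CM/procedures end date is available, this will be used as the latest possible AE/CM/procedures occurrence date in the imputation range". Three branches then apply in order.

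1. "If the active treatment start date falls within imputation range, incomplete AE/CM/procedures start date will be imputed as the active treatment start date".
2. If the active start is outside the range "and the placebo treatment start date falls within the imputation range, an incomplete AE/CM/procedures start date is imputed as the placebo treatment start date".
3. "Otherwise, the partially missing AE/CM/procedures start date will be imputed to the earliest date of the imputation range".

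For the placebo arm, Protocol 6.1 states that "120 mg elinzanetant will be administered from week 13 to 52 and optionally for additional 2 years". SAP 4.1.2 dates that switch by the first phase 2 study-drug intake in the eCRF.

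The intercurrent event for prohibited medication is built from medication start and stop dates (footnotes to the tables in SAP 6.4.3). Many of the listed drugs count only if started, changed or stopped in the first 12 weeks. SAP 4.1.2 flags events up to Day 84 and assigns them to weeks as follows: "if the ICE occurs on or before the 5th day of the week, it will be flagged for the respective week"; an onset on the 6th or 7th day counts from the next week. SAP 6.4.3 has no date rule of its own, and SAP 6.5.5 refers partial medication dates to 4.1.1.

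On timing, SAP 4.2.1 says "All the ICEs will be reviewed prior to study unblinding". SAP 6.4.3 says that the list of prohibited drugs and their assumed effect periods "will be reviewed during blind review of the data and finalized prior to unblinding".

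**The concern.** For an adverse event, dating to the active start is a cautious choice, because it attributes the event to the drug. For a concomitant medication in the placebo arm it does something different: it moves the record past Day 84 and out of the placebo-controlled comparison. The same incomplete record in the elinzanetant arm stays inside the 12-week window.

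The supplementary estimands are exposed. SAP 4.2.3 handles prohibited medication by the hypothetical strategy in the first (affected data discarded and modelled) and by the composite strategy in the second (zero change assigned). SAP 4.3.1.4 applies both to the key secondary endpoints as well. A flag raised in one arm only removes or overwrites observed data in that arm only. Under the composite strategy this would usually count against elinzanetant. The by-arm event counts and the Kaplan-Meier plot for prohibited medication in SAP 4.1.3 use the same dates. For the affected records one must also know the allocation to know which date is the active start, although the events are meant to be reviewed blinded.

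**Working it through.** The plan states no figure for this rule. Its own week-flag example in SAP 4.1.2 can be reproduced: the 2nd day of Week 4 (Day 23) gives Week 4, and the 6th day (Day 27) gives Week 5.

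**Inputs**
- Active start: Day 1 on elinzanetant; the switch day S on placebo. S = 85 to 90 is assumed from the T6 visit window in Protocol Table 1-2. The SAP uses the actual intake date.
- Week 12 = Days 78-84 (SAP 4.1.2.1). Its 5th day is Day 82, so the latest onset that flags Week 12 is Day 82.
- The drug is ongoing, or at least not known to have ended before S.

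**Worked example.** First dose 20 Mar 2023, so Day 85 is 12 Jun 2023.

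| Recorded start | Elinzanetant | Placebo, switched |
|---|---|---|
| 2023 | Day 1, event | Day 85, no event |
| JUN 2023 | 1 Jun = Day 74, event | 12 Jun = Day 85, no event |
| MAY 2023 | 1 May = Day 43, event | Day 43, event |
| MAR 2023 | Day 1, event | Day 1, event |

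The arms differ in the first two rows, where the range contains the switch date. In the June row the elinzanetant date comes from the earliest-date branch, not from the active start.

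**Switch-month dates, formula.** If the switch falls on calendar day d of a 30-day month, the first of that month is study day S - (d - 1). On elinzanetant it flags Week 12 if S - (d - 1) <= 82, i.e. d >= S - 81. With d uniform on 1 to 30, the share is (112 - S)/30:
- S = 85: 27/30 = 90%
- S = 86: 26/30 = 87%
- S = 90: 22/30 = 73%

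On placebo the record is dated at S, after Day 84, so the share is 0/30.

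**Check by enumeration.** Both rules were applied to identical records in each arm for every first-dose date from 1 Sep 2022 to 31 Dec 2023 (illustrative dates). Entries are records that are an event on elinzanetant only.

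| Record | S = 85 | S = 90 |
|---|---|---|
| Month only, switch month | 439/487 (90%) | 359/487 (74%) |
| Month only, first-dose month | 0/487 | 0/487 |
| Month only, month in between | 0/857 | 0/937 |
| Year only, first dose and switch in that year | 319/319 | 309/309 |
| Year only, switch year, first dose the year before | 162/168 | 162/178 |
| Year only, first-dose year, switch the year after | 0/168 | 0/178 |
| Year only, known end on Day 70 | 0/319 | 0/309 |

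No record was an event on placebo only.

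**The case against.** Most of the case on the other side limits the scope, and most of it stands.

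- **Few records may be affected.** Protocol 6.8 requires start and end dates for every medication, and Protocol Table 1-2 has contacts at Weeks 2, 4, 6, 8, 10, 12 and 16. A year-only start for a drug begun between such contacts is unlikely. The 73% to 90% are conditional on a record whose frequency the documents do not give.
- **Rescue treatment.** A reader might infer that alternative treatment for vasomotor symptoms after stopping study drug is also dated asymmetrically. The documents do not support this for discontinuation in Phase 1. Under SAP 4.1.2 such a placebo participant never receives phase 2 drug, so there is no active start, and the fallback branches give the same date as on elinzanetant.
- **Blinding.** The finalisation statement in SAP 6.4.3 concerns the drug list and effect periods, not participant-level flags, and SAP 4.2.1 says only that events are reviewed. SAP 6.4.3 also provides for manual review. A blinded reviewer can see both candidate dates, since first phase 2 intake is in the eCRF. What remains is narrower: for the affected records the reviewer cannot tell which date the rule selects. It would be wrong to infer that the intercurrent events as a whole cannot be derived blinded, because the other partial dates do not depend on allocation.

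None of this removes the asymmetry. Manual review is given no alternative rule for partial dates.

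**Conclusion.** The point holds in a limited form and is minor. It applies to prohibited drugs in participants who switched from placebo (against the same record on elinzanetant), where the drug is not known to have ended before the switch and its start is known only to the switch month or to the year of the switch. For these records the rule produces an event on elinzanetant only, never the reverse: about 73% to 90% of switch-month dates for a switch on Day 90 to Day 85, and every year-only date that contains both starts.

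A reader might infer that the primary result is biased. It is not: SAP 4.2.1 applies treatment policy to every intercurrent event, and SAP 4.3.1.2 handles the key secondary endpoints in the same way. The effect is confined to the two supplementary estimands, the by-arm counts and the Kaplan-Meier plot for prohibited medication. Its size is proportional to a number of records that is not stated and is probably small. The conclusion assumes that the 4.1.1 rule governs the dates used in 6.4.3, which does not cite it; the link runs through 6.5.5 and the absence of any other rule.

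**What to change.** Keep the active-start rule in SAP 4.1.1 for adverse events. For concomitant medication and procedures, set a partial start date to the first study-drug intake in either arm if that lies in the range, and otherwise to the earliest date in the range. State in 6.4.3 that the intercurrent-event flags use these dates. In the worked example the year-only record then falls on Day 1 and the June record on Day 74 in both arms, and the dates can be derived without the allocation.

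The cost is one sentence in 4.1.1, a cross-reference and a small programming change; adverse event analyses are unchanged. There is one downside. A stable drug begun before the study in the same calendar year, with only the year recorded, may be dated to Day 1 and look newly started. That would happen equally in both arms, and the blinded manual review can resolve it.
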